11.5.1.9. Grading of Adverse Event Severity

In this study the severity/intensity of AEs will be graded using the Common Terminology Criteria for Adverse Events (CTCAE, Version 5.0) of the US National Cancer Institute [21].

For each event, changes in severity grade and seriousness criteria should be recorded.

For adverse events not reported in the CTCAE Version 5.0, the Investigator will use the Grade or adjectives reported in [Table 12](#)

Table 12. Grading of Adverse Event Severity for events not reported in the CTCAE v 5.0

Grade	Adjective	Description
Grade 1	Mild	Does not interfere with patient's usual function
Grade 2	Moderate	Interferes to some extent with patient's usual function
Grade 3	Severe	Interferes significantly with patient's usual function
Grade 4	Life-threatening	Results in threatening to life or in an incapacitating disability
Grade 5	Death	Results in death

Note the distinction between the term “serious” and “severe”, which are not synonymous. The term “severe” is used to describe the intensity of a specific event (i.e., severe headache) while the term “serious” is based on patient/event outcome or action criteria. Seriousness (not severity) serves as a guide for defining regulatory reporting obligations. For example, vomiting Grade 1 for which a hospitalization occurred is a serious event even if the event is not severe.

11.5.1.10. Exposure In Utero

If a female patient becomes or is found to be pregnant while receiving the study drug or within 180 days from its discontinuation, the Investigator should transmit this information using the Part I of Exposure in Utero (EIU) Form to the Sponsor Pharmacovigilance. This must be done irrespective of whether an adverse event has occurred and within 24 hours of awareness of the pregnancy. However, if the patient begins a new anticancer therapy before 90 days after the last dose of study treatment administration, the exposure “in utero” reporting period will end at the time the new treatment is started.

The Investigator will follow the patient until completion of the pregnancy or until pregnancy termination (i.e., induced abortion) and then notify the Sponsor of the outcome within 5 days or as specified below. The Investigator will provide this information completing Part II of EIU form. The reason(s) for an induced abortion must be specified.

If the outcome of the pregnancy meets the criteria for immediate classification as a serious adverse event (i.e., spontaneous abortion, stillbirth, neonatal death, or congenital anomaly [including that in an aborted fetus]), the Investigator should follow the procedures for reporting serious adverse events, i.e., report the event to the Sponsor (as described in Section [11.5.1.7](#))

In the case of a live birth, the “normality” of the newborn can be assessed at the time of birth (i.e., no minimum follow-up period of a presumably normal infant must pass before an Exposure in Utero Form can be completed). The “normality” of an aborted fetus can be assessed by gross visual inspection unless pre-abortion laboratory findings are suggestive of a congenital anomaly.

Other pregnancy outcomes that are classified as SAEs:

- “Spontaneous abortion” includes miscarriage and missed abortion.
- All neonatal deaths that occur within 1 month of birth should be reported, without regard to causality. In addition, any infant death after 1 month that the Investigator assesses as possibly related to the “in utero” exposure to the study drug should also be reported.

If a female partner of a male patient taking the IMP becomes pregnant while the male patient is still on IMP or within 90 days after last dose of IMP, the male patient taking IMP should notify the Investigator, and the pregnant female partner should be advised to call her healthcare provider immediately. If a pregnancy related event is reported in a female partner of a male patient, the Investigator should ask if the female partner is willing to share information with the Sponsor and allow the pregnancy related event to be followed up to completion.

The Investigator has to submit the information of pregnancy or suspect pregnancy of a female partner of a male patient to the Sponsor Pharmacovigilance by e-mail or by fax, using the EIU Form, within 24 hours from his/her awareness of the event.

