3. BACKGROUND INFORMATION AND STUDY RATIONALE

3.1. Disease background

Primary liver cancer is the 6th most common neoplasm and among the leading cause of cancer-related deaths worldwide. Hepatocellular carcinoma (HCC) constitutes 80-90% of all primary liver cancers [1, 2].

The incidence is increasing and will soon surpass one million annual cases worldwide with an age-adjusted incidence of 10.1 cases per 100,000 person-years. In 2019 the estimated incidence in US was 42.030 new cases/year diagnosed with estimated disease related deaths of 31.780. The disease is more frequent in males than in females, in the ratio of 2.4:1 [1, 2].

According to the Italian Cancer Registry, in 2018 12.800 new cases of HCC were documented in Italy. The prognosis of the disease is poor with a 5-years survival rate of only 18-20% based on US and Italian cancer registry data [1, 2].

HCC most common etiological factor in the world is hepatitis B virus (HBV) infection. The worldwide incidence is heterogeneous because of the variable prevalence of risk factors. Almost 80% of HCC cases occur in sub-Saharan Africa and eastern Asia and the major risk factors here are hepatitis B and aflatoxin exposure, whereas hepatitis C and Non-alcoholic fatty liver disease (NAFLD) is the primary risk factor in the USA, Europe, and Japan. The development of cirrhosis is associated with high risk for developing HCC [3, 4].

Coexistence of cancer and cirrhosis in HCC is an essential hallmark that has shaped clinical trial design over the time and is outlined in the Barcelona Clinic Liver Cancer (BCLC) algorithm.

The BCLC staging system is an effective, integrated system that takes into account the patient performance status (PS), tumor burden, vascular involvement, potential hepatic dysfunction, and portal hypertension [5].

At early stages of HCC (BCLC stage 0/A), treatment strategies are potentially curative and include liver resection, liver transplantation, and ablation. At intermediate stages (BCLC stage B), palliative locoregional therapies such as transarterial chemoembolization (TACE) remain the gold standard for treatment. However, most HCC cases are diagnosed at advanced stages (BCLC stage C) when curative therapies or TACE are no longer applicable [5].

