**Calculated using the Cockcroft-Gault equation (mL/min): $(140 - \text{age}) \times \text{weight (kg)} / (\text{serum creatinine [mg/dL]} \times 72)$ for males. (For females multiply by 0.85)

10. In case of active hepatitis B (HBV) or chronic HIV infection the patient should receive antiviral therapy per local standard of care.
11. Patients must use effective contraception or abstinence. Female subjects must be surgically sterile or, if subjects of childbearing potential, must agree to use effective contraception (see [Appendix 6](#)) or abstinence during the period of therapy and in the following 180 days after discontinuation of study treatment. Male subjects must be surgically sterile or must agree to use effective contraception or abstinence during the period of therapy and in the following 90 days after discontinuation of study treatment.
12. With the exception of alopecia, resolution of all acute toxic effects of any prior systemic therapy, surgery or radiotherapy to NCI CTC (Version 5.0) Grade ≤ 1 or to the baseline laboratory values as defined in Inclusion Criterion Number 9.
13. Able and willing to comply with scheduled visits, therapy plans, and laboratory tests required in this protocol.
14. Signed and dated IEC-approved Informed Consent Form indicating that the subject is aware of the neoplastic nature of his/her disease and has been informed of the procedures to be followed, the investigational nature of the therapy, potential benefits, side effects, discomforts, risks and alternative treatments.

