20. Tumor imaging: to be performed at screening, within 28 days from treatment start (in case a tumor imaging is already available in the specified time window, it has not to be repeated); at the end of even months (even cycles) of treatment and at EoT. The EoT assessment is to be performed only if it was not performed in the previous 4 weeks. In patients withdrawn for reasons other than progressive disease (PD), during follow up, tumor assessment should be performed every 2 months, until PD or until a new antitumor therapy starts. On treatment, a time window of -2/+5 days is allowed. Patients with responding tumors (complete or partial response) must have response confirmed by CT scan at least 4 weeks after the 1 st documentation of response. The same method of assessment and technique should be used to characterize and follow the same lesion at screening, during treatment and at EoT. Ct scan is the desirable method for lesion measurement (see Section 11.3.1).
21. BCLC and TNM Staging: TNM and BCLC staging will be requested at enrollment for all patients, including collection of clinical related additional info
22. Survival follow up: post-treatment survival status, including additional information (e.g. new anticancer therapy), will be collected at the 28-days follow up visit and thereafter every 2 months from last treatment administration until death. Telephone contacts are acceptable for these assessments.
23. Biomarkers sampling: peripheral blood samples will be collected at Enrollment (≤ 7 days before Cycle1 Day1) for analysis of selected molecular alterations in circulating free DNA (cfDNA) from plasma
24. PK blood sample: during the Phase II, a sparse sampling procedure will be adopted; blood sampling for PK is to be performed at cycles 1, 2, 3 and 4 (refer to Table 5 for details).
25. End of Treatment (EoT): visit to be performed within 7 days from the decision of discontinuing the study drug.
26. Off treatment assessments: 28 days, and no more than 35 days, after discontinuation of study treatment patients will return for the following assessments: ECOG PS, blood pressure and heart rate, hematology, blood chemistry, coagulation, concomitant medications, adverse events and survival follow up. Further follow up contacts will be scheduled every 2 months from last treatment administration, until death, to assess the survival status, including possible additional information.

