11.5.1.4. Adverse Event Reporting Period

The adverse event reporting period for this trial begins upon signing of informed consent and ends 28 days after the last study treatment administration.

However, if a patient begins a new anticancer therapy earlier than 28 days after the last dose of study treatment administration, the adverse event reporting period will end at the time the new anticancer therapy starts.

All the adverse events that occur in trial patients during the adverse event reporting period must be reported to the Sponsor, whether or not the event is considered related to the study treatment.

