11.5.1.5. Adverse Event Follow Up after the End of the Reporting Period

The following events should be followed after the end of the reporting period (i.e., 28 days after the last study treatment administration):

1. SAEs with outcome ‘not recovered’ or ‘unknown’ at the end of the reporting period.
2. Non-serious events classified as related to the investigational study treatment with outcome ‘not recovered’ or ‘unknown’ at the end of the reporting period.

These events should be followed until they resolve or until the Investigator determines, whenever possible, that they have become “chronic” or “stable”. Resolution of such events is to be documented on the SAE Form and/or on e-CRF.

In addition, if after the end of the reporting period, suspected serious adverse reactions or deaths are reported to the Investigator and he/she believes that they are related to the IMP, it is the Investigator’s responsibility to report these suspected serious adverse reactions to the Sponsor. Such suspected serious adverse reactions will be reported using a Serious Adverse Event Report or by any other way chosen by the Investigator.

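### Pregnancy reporting for female patients should run 180 days, but stops early if a new anticancer therapy starts before day 90, a threshold that does not fit the window

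*Protocol*

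**What the plan says.** Protocol Section 11.5.1.10 obliges the investigator to notify the sponsor within 24 hours of awareness if a female patient "becomes or is found to be pregnant while receiving the study drug or within 180 days from its discontinuation". The duty applies whether or not there is an adverse event. The window equals the contraception period for women in Section 6.1, criterion 11, which asks for effective contraception or "abstinence during the period of therapy and in the following 180 days after discontinuation of study treatment".

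The same paragraph then makes an exception: "However, if the patient begins a new anticancer therapy before 90 days after the last dose of study treatment administration", the in utero reporting period closes when that therapy starts. Nothing is said about a therapy begun at day 90 or later, so on a literal reading the 180 days stand.

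Three neighbouring rules help in judging the exception:

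- Section 11.5.1.4 closes adverse event reporting early "if a patient begins a new anticancer therapy earlier than 28 days after the last dose of study treatment administration". The window there is also 28 days.
- The partner rule in Section 11.5.1.10 applies if the partner "becomes pregnant while the male patient is still on IMP or within 90 days after last dose of IMP". It has no cut-off for new therapy.
- Section 11.5.1.5 keeps a duty to report after the period ends if "suspected serious adverse reactions or deaths are reported to the Investigator and he/she believes that they are related to the IMP".

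The SAP does not address pregnancy reporting periods.

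**The concern.** The exception undoes part of the rule that it follows. A woman who moves to another anticancer drug soon after her last dose is the one most recently exposed, and she loses the most reporting time. One who waits until day 90 keeps all of it.

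The trigger covers pregnancies that are found as well as those that begin in the window. The last scheduled pregnancy test is at the end-of-treatment visit, within 7 days of the decision to stop. A conception late in treatment may be too early to detect then. If it is first recognised after an early switch, the period has already closed, although the fetus was exposed to study drug.

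The protocol's own risk statements support the full window. Section 3.4 reports micronuclei in human lymphocytes in vitro (with a negative Ames test), Section 9.1.3 treats the drug as cytotoxic, and Appendix 6 warns that hormonal contraception may lose efficacy on treatment. What is at stake is the completeness of safety information on exposed pregnancies.

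**Working it through.** **Inputs.** Reporting window W = 180 days and threshold T = 90 days, both from Section 11.5.1.10. The window runs from discontinuation and the threshold from the last dose; I take these as the same day. Let s be the day on which a new anticancer therapy starts, counted from the last dose. The plan states no figure for lost reporting time, so there is none to reproduce.

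**Rule as written.** Reporting lasts s days if s < 90, and 180 days if s ≥ 90 or there is no switch. The loss is therefore 180 − s for s < 90, and 0 otherwise.

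| Switch day | Days lost, current text | Days lost if 90 became 180 | Days lost if the exception is deleted |
|---|---|---|---|
| 30 | 180 − 30 = 150 | 150 | 0 |
| 60 | 180 − 60 = 120 | 120 | 0 |
| 89 | 180 − 89 = 91 | 91 | 0 |
| 90 | 0 | 180 − 90 = 90 | 0 |
| 120 | 0 | 180 − 120 = 60 | 0 |

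Two women who switch one day apart, on days 89 and 90, differ by 91 reporting days under the current text.

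**Comparison with the neighbouring rules.**

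- Adverse events: threshold 28, window 28, ratio 1. Pregnancy in female patients: threshold 90, window 180, ratio 0.5.
- Partners of male patients: 90 days with no cut-off. If therapy changes at day 30, a male patient's partner stays covered to day 90, while a directly dosed woman is covered only to day 30.
- If the purpose were to avoid doubtful attribution once a second drug is on board, the cut-off would also apply from day 90 to day 180. It does not. The duty also rests on exposure, not on judged causality.

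**Number of women.** Section 3.1 states: "The disease is more frequent in males than in females, in the ratio of 2.4:1". If that ratio held in Phase II, capped at 40 patients, the expected number of women would be 40 / (2.4 + 1) = 11.8, about 12. Only some would be of childbearing potential. The protocol gives no rate of switching, so the number who would switch before day 90 cannot be derived.

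**The case against.** The strongest reply is that the consequence is small. An affected patient must be of childbearing potential, start new therapy before day 90, and become or be found pregnant before day 180 despite a contraception duty that has no new-therapy exception. Her protection is unchanged; only notification of the sponsor is affected. This stands, and it limits the weight of the point.

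Second, ending collection at a new anticancer therapy is a repeated convention in this protocol, so the anomaly may be only the number 90. The convention is real, but the partner rule does not follow it, and aligning the threshold with the window would reduce reporting for switches from day 90 to day 179.

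Third, other rules catch some cases. Section 11.5.1.10 separately asks for neonatal deaths within a month of birth and for later infant deaths possibly related to exposure, and a congenital anomaly believed related would fall under Section 11.5.1.5. Whether the infant-death provisions survive the early close is open to interpretation. None of these covers an uncomplicated pregnancy, or a serious outcome short of death that the investigator does not think related.

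Fourth, the documents give no half-life, so a conception late in the 180 days is not shown to be exposed. That is fair, but the protocol chose 180 days itself, and the argument does not apply to a conception on treatment that is found late.

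Fifth, detection after the end-of-treatment visit is passive, so deleting the exception finds no additional pregnancies. This is true. The duty is triggered by awareness, however, and the exception tells a site that is aware of a pregnancy that it need not report it.

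**Conclusion.** The point holds. The 90-day threshold does not fit its own 180-day window, nothing else in the protocol or SAP reconciles the two, and no reason is given. A switch before day 90 removes between 91 reporting days (day 89) and 150 (day 30) in the cases worked above, and more for a still earlier switch; a switch at day 90 or later removes none.

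This rests on reading the exception literally and on treating discontinuation and last dose as the same day. The losses are calendar days of a reporting duty, not counts or shares of pregnancies. The estimate of about 12 women assumes that the general HCC sex ratio carries over to this trial. The 90 may have been carried over from another rule, but the documents do not show that.

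The effect is confined to safety reporting; eligibility, dosing, the response rate analysis and sample size are unaffected. The change is worth making because it is cheap and each report of an exposed pregnancy is rare.

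**What to change.** In Section 11.5.1.10, delete the sentence that closes reporting at a new anticancer therapy begun before day 90, so that the 180-day window applies to every female patient. Record any new anticancer therapy and its start date on Part I of the Exposure in Utero form, if it is not already there (the form is not among the documents). Do not simply replace 90 with 180: a switch at day 120 loses no reporting days now and would then lose 60.

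The cost is one deleted sentence and at most one added form item. No visit is needed, because under Section 7 post-treatment survival status, with additional information such as new anticancer therapy, "will be collected at the 28-days follow up visit and thereafter every 2 months from last treatment administration until death". Those contacts do not name pregnancy. A question about it could be added to them if the sponsor wants active detection, but the correction does not depend on it.

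The downsides are a few reports with exposure to two drugs, and a departure from the convention that reporting stops at new therapy.

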11.5.2. Laboratory Safety Assessments

Laboratory safety assessments will include repeated evaluation of hematology, biochemistry and coagulation parameters, urinalyses and pregnancy test, according to timing reported in Section 7, Schedule of Events (Table and related footnotes). Investigators may order additional blood tests for planning treatment administration, dose modification, or further evaluation of adverse events.

The following laboratory parameters will be used to monitor safety:

- *Hematology* (local laboratory) includes: hemoglobin (Hb), red blood cells (RBC), platelet (PLT) and white blood cells (WBC) with differential count (neutrophils, lymphocytes, monocytes, eosinophils and basophils). The assessment is mandatory, at screening (≤ 7 days from treatment start). During treatment on Phase I, hematology should be done from cycle 1 to cycle 3, on days 1, 8, 15, 22 and, from cycle 4 onward, on days 1, 8, 15; during treatment on Phase II, hematology should be done on cycle 1, on days 1, 8, 15, 22; from cycle 2 onward, on days 1, 8, 15; at cycle 2, in case neutropenia Grade ≥ 2 is observed, repeat the hematological evaluation also at day 22. In case of cycle delay due to toxicity and/or if clinically indicated, additional assessments should be done as per medical judgment; hematology should be repeated at the start of the delayed cycle. All hematology assessments performed during the treatment period can be done the day before the scheduled one; on days of treatment administration, sampling should be performed and results should be available before the start of NMS-01940153E infusion. Hematology should be performed also at end of treatment (EoT) and 28-days follow up visits. Note: at Cycle 1 Day 1, hematology does not need to be repeated before study drug administration if it was performed at screening within 24 hours from treatment start.

- *Blood chemistry* (local laboratory) includes: glucose, electrolytes (Na, K, Ca, P, magnesium), urea or BUN (Phase II), serum creatinine, creatinine clearance (calculated with Cockcroft-Gault equation), total protein, albumin, aspartate aminotransferase (AST/SGOT), alanine aminotransferase (ALT/SGPT), gamma-GT, total bilirubin, unconjugated bilirubin, alkaline phosphatase (ALP), lactate dehydrogenase (LDH). The assessment is mandatory, at screening (≤ 7 days from treatment start). During treatment on Phase I, blood chemistry should be done from cycle 1 to cycle 3, on days 1, 8, 15, 22 and, from cycle 4 onward, on days 1, 8, 15; during treatment on Phase II, blood chemistry should be done on cycle 1, on days 1, 8, 15, 22 and, from cycle 2 onward, on days 1, 15. In case of cycle delay due to toxicity and/or if clinically indicated, additional assessments should be done as per medical judgment; blood chemistry should be repeated at the start of the delayed cycle. All blood chemistry assessments performed during the treatment period can be done the day before the scheduled one; on days of treatment administration, sampling should be performed, and results should be available before the start of NMS-01940153E infusion. Blood chemistry should be performed also at EoT and 28-days follow up visits. Note: at Cycle 1 Day 1, blood chemistry does not need to be repeated before study drug administration if it was performed at screening within 24 hours from treatment start.
- *Coagulation* (local laboratory) includes international normalized ratio (INR) of prothrombin. The assessment is mandatory, at screening (≤ 7 days from treatment start). During treatment on Phase I, coagulation should be done from cycle 1 to cycle 3, on days 1, 8, 15, 22 and, from cycle 4 onward, on days 1, 8, 15; during treatment on Phase II, blood chemistry should be done on cycle 1, on days 1, 8, 15, 22 and, from cycle 2 onward, on days 1, 15. In case of cycle delay due to toxicity and/or if clinically indicated, additional assessments should be done as per medical judgment; coagulation should be repeated at the start of the delayed cycle. All coagulation assessments performed during the treatment period can be done the day before the scheduled one; on days of treatment administration, sampling should be performed, and results should be available before the start of NMS-01940153E infusion. Coagulation should be performed also at EoT and 28-days follow up visits. Note: at Cycle 1 Day 1, coagulation does not need to be repeated before study drug administration if it was performed at screening within 24 hours from treatment start.
- *Urinalysis* (local laboratory) includes: pH, glucose, protein and blood. The assessment is mandatory, at screening (≤ 7 days from treatment start) and at EoT visit. If clinically indicated, additional assessments should be done as per medical judgment.
- *Serum/Urine Pregnancy Test* (local laboratory). It is indicated only for women of child-bearing potential. Phase I: the assessment should be done at screening, within 72 hours from treatment start, and at EoT visit. Phase II: the assessment should be done at screening, within 72 hours from treatment start, on day 1 of each treatment cycle (before treatment administration), and at EoT visit. Note: at Cycle 1 Day 1, pregnancy test does not need to be repeated before study drug administration if it was performed at screening within 24 hours from treatment start.

- *Serology*: in case of positive HBV anamnesis, includes HBV DNA; in case of positive HCV anamnesis, includes HCV RNA; in case of HBV unknown anamnesis, includes HbsAg, HbeAg, HbcAg, Anti-HBc-IgM; in case of HCV unknown anamnesis, includes liver function test as by local standards and HCV Ab. Anti-HIV test. To be performed at screening, within 7 days from treatment start.

In case hematology, blood chemistry and coagulation have not recovered at the end of last cycle, they should be followed-up for 28 days after the last study treatment administration or until they resolve or the Investigator assesses them as chronic or stable, or until alternative anticancer therapy is initiated. In the latest case, the reporting period will end at the time the new treatment is started. If the laboratory value is abnormal, clinically significant and evaluated as drug related after the 28 days follow-up assessment, it has to be reported only as adverse event and as such followed until it resolves or the Investigator assesses it as chronic or stable, or until alternative anticancer therapy is initiated.

